### ***MAC-LD Diagnosis Dates***

If the reported date is partially missing, the following imputation rules will be applied:

- the 15th of the month, if only the day is missing.
- the 30th of June, if only the year is available.
- No imputation if completely missing.

### ***Concomitant Medication Dates***

In case of partially missing concomitant medication start/end dates, the following imputation rules will be applied:

- the 15th of the month, if only the day is missing.
- the 30th of June, if only the year is available.
- if the imputed start date is after the concomitant medication end date, further adjustment of the imputed start date is required. It will be imputed as the concomitant medication end date
- No imputation if completely missing.

If the medication was taken prior to study start (Day 1) based on eCRF question, and the imputed start date is after first treatment date, further adjustment of the imputed start date is required. It will be imputed as the day prior to first dosing date.

If the medication was taken after study start (Day 1) based on eCRF question, and the imputed start date is prior to first dosing date, the imputed start date will be further adjusted to be the first study treatment dosing date. The partially missing medication end date will be imputed following the rule described at the beginning of this section to ensure it is on or after first dosing date, and after its start date.

In case of a completely missing start date, the concomitant therapy will be considered as having started before the trial, unless the eCRF indicating that the medication was taken after study start.

In case of a completely missing end date, the concomitant therapy will be considered as ongoing at the end of the trial, unless the eCRF indicating not ongoing.

### 5.1.1. Visit Windows

As participants do not always adhere to the protocol visit schedule, the following rules are applied to assign actual visits to analysis visits. Listed below are the visit windows and the target days for each visit. The reference day is Study Day 1. If a participant has 2 or more actual visits in 1 visit window, the visit closest to the target day will be used as the protocol visit for that visit window. The other additional visit(s) will not be used in the summaries or analyses but they can be used for determination of clinically important endpoints. If 2 actual visits are equidistant from the target day within a visit window, the later visit is used.

All assignments will be made in chronological order. Once a visit date is assigned to a visit window, it will no longer be used for a later time point except for the endpoint. Listed below (Table 2 and Table 3) are the analysis visit windows and the target days for each visit defined in the protocol.

Start date in the investigation phase is defined as the date of first study intervention intake. All efficacy and safety assessments during the investigation phase will be assigned an analysis study day relative to this date.

The investigation phase study day in the investigation phase (ADY) is defined as:

$$\text{ADY} = \text{visit date} - \text{investigation phase start date} + 1$$

For visits on or after investigation phase Day 1, and

$$\text{ADY} = \text{visit date} - \text{investigation phase start date}$$

For visit before investigation phase Day 1 (screening phase).

The optional investigation phase study day in the optional investigation phase (ADY) is defined as:

$$\text{ADY} = \text{visit date} - \text{optional investigation phase start date} + 1$$

For visits on or after optional investigation phase Day 1.

All efficacy and safety assessments during the Follow-up (FU) phase will be assigned a day relative to FU start date. The FU study day in the FU treatment phase (ADY) is defined as:

$$\text{FU ADY} = \text{visit date} - \text{FU start date} + 1$$

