- w. Examination of height (screening only), body weight measurement, observation for skin events/reactions, assessments performed as part of the clinical course of NTM related disease (body temperature, heart rate, respiratory rate, and oxygen saturation) and additional assessments (systolic blood pressure and diastolic blood pressure). Physical examination and vital signs will be performed before intake of study intervention and blood sampling.
- x. Including hematology, chemistry and urinalysis.
- y. Including visual acuity, color discrimination, visual field. Audiology and visual examinations within 4 week prior to Day 1 and within 4 days prior or after each visit other than Day 1 will be acceptable.
- z. After Week 24 assessment, all participants in the Group B who are non-conversion and well-tolerated, will be considered to receive the BDQ-containing regimen at the discretion of the investigators. When the investigator changes to BDQ-containing regimen, 2-week washout of treated rifamycin must be given before initiation of BDQ-containing regimen. The investigators can postpone the decision to transfer

to the optional cohort for up to Week 32 in order to confirm a sputum culture positive at Week 24, if necessary. If decision to transfer to the optional cohort exceeds Week 32 for reasons such as time required to obtain the result of microbiology assessment of Week 24, the period may be extended. If necessary, consider study date of OPD1 by adding the number of days required to switch to the optional cohort to study date of Week 24.

- aa. OPD1 is Day 1 for participants who are transferred to optional cohort. Assessments planned on OPD1 must be performed prior to first dose of BDQ. The investigators can postpone the decision to switch to the optional cohort for up to Week 32 in order to confirm sputum culture positive at Week 24. If decision to transfer to the optional cohort exceeds Week 32 for reasons such as time required to obtain the result of microbiology assessment of Week 24, the period may be extended.
- bb. Upon completion of the 48-week optional treatment period, the observation of each participant will be completed.

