##### ***AST and/or ALT Elevation***

$<5.0 \times$  ULN AST or ALT elevation with normal bilirubin:

Participants may continue to take the study intervention. Participants should be followed until resolution (return to baseline) or stabilization of AST/ALT elevation. Clinical symptoms, AST,

ALT, and serum bilirubin should be monitored every 2 weeks until clinically stable as necessary to manage the participant's condition.

$\geq 5.0 \times \text{ULN}$  but  $\leq 8.0 \times \text{ULN}$  AST or ALT elevation or  $\geq 3 \text{ ULN}$  accompanied by bilirubin  $\geq 2.0 \times \text{ULN}$ :

Participants will be permanently discontinued from treatment of the suspected causative background agent or temporarily withhold study intervention at the investigator's discretion. Clinical symptoms, AST, ALT, and serum bilirubin should be monitored every 2 weeks until clinically stable as necessary to manage the participant's condition. If ALT, AST, and bilirubin do not improve or worsens within 2 weeks, the study intervention will be temporarily withheld for up to 2 weeks per investigator discretion. Additional tests should be performed to evaluate the cause of hepatitis (eg, hepatitis A, B, C). Liver enzymes, including serum bilirubin should be monitored as frequently as necessary to manage the participant's condition. If AST/ALT decreases to  $< 5.0 \times \text{ULN}$ , study intervention can be restarted once. Participants who fail to show improvement, demonstrated by no improvement in clinical course or persistent AST and ALT  $\geq 5.0 \times \text{ULN}$  values, or persistent AST/ALT  $\geq 3.0 \times \text{ULN}$  accompanied by bilirubin  $\geq 2.0 \times \text{ULN}$  (over 4 weeks) will have to permanently discontinue the study intervention. Participants should be followed until resolution or stabilization (return to baseline) of AST/ALT/bilirubin elevation.

$> 8.0 \times \text{ULN}$  AST or ALT elevation

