    - Some or all of the lung function assessments, as well as CT scan, may be obtained on a different date from the visit if not available at the visit. Deviations due to missed tests are allowed in situations where the assessment themselves cannot be performed
    - Triplicate ECGs are required; however, if triplicate ECGs are difficult for any reason, duplicate ECGs or single ECG are acceptable
    - Visual and/or auditory examinations may be performed on different day(s) from the visit date. In addition, this examination(s) may be omitted only if the subject does not complain of any visual or auditory abnormalities
  - If any deviation other than the above may be occurred, the investigator or co-investigator will promptly report it to the sponsor and consider necessary measures.

- Unperformed tests, assessments, or visits will be recorded as a protocol deviation in the clinical trial management system. Discontinuation of investigational product treatment and withdrawal from the study must be documented on the case report form (CRF) preceded by the words "COVID-19 -related".
  - Other relevant study data affected by the pandemic will also be recorded/displayed as "COVID-19 -related" on the CRF and/or other study systems, as per sponsor guidance. This may include missing/late/visit modification/assessment/investigational product administration and temporary actions as described above.
- The sponsor will assess the overall impact of COVID-19 on the collection of critical study data and will provide details of the additional data analyses in the study SAP (Statistical Analysis Plan), if needed.
- Exclusion: Subjects with confirmed SARS-CoV-2 (COVID-19) infection (eg, positive PCR test) or strongly suspected SARS-CoV-2 infection (No test results recorded but clinical features present) within 4 weeks before informed consent are basically excluded from the study. However, patients who meet the following criteria 1 and 2 and in whom a validated SARS-CoV-2 test result has been recorded as negative can be enrolled in the study; however, the eligibility will be determined after carefully monitoring the conditions of candidate patients.
  1. A negative test result was obtained at least 2 weeks after disappearance of the condition presumed to be due to SARS-CoV-2 infection (Key Clinical Features [eg, fever, cough, dyspnea, etc.])  
  
and
  2. No SARS-CoV-2 infection or strongly suspected infection occurs during the screening period after a negative test result

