### **5.6.3. Additional Safety Assessments**

#### **5.6.3.1. Clinical Laboratory Tests**

Clinical laboratory tests will be displayed for the participants included in the safety analysis set.

Descriptive statistics (n, mean, SD, minimum, median and maximum) and graphical displays will be presented for chemistry, hematology, and urinalysis laboratory tests at scheduled time points by intervention arm and study phase.

Change/percent change from baseline to each scheduled time point will be summarized for chemistry, hematology, and urinalysis tests and displayed by intervention group.

An abnormality (toxicity grade and/or abnormality based on normal ranges) will be attributed to the baseline and postbaseline values.

Postbaseline abnormalities will be compared with their corresponding baseline result:

- For toxicity grades, treatment emergent (TE) will be concluded if the postbaseline value is worse than the baseline value.
- For abnormalities based on normal range and/or criteria: If the postbaseline value is above the upper limit and the baseline value is below the upper limit (eg, Normal or Low), then the postbaseline abnormality will be considered TE. The same applies to the postbaseline value being below the lower limit with the baseline value being above the lower limit (eg, Normal or High).
- If the baseline value is missing, a postbaseline abnormality will always be considered as TE.

Number and percentage of participants with clinically important laboratory values and/or markedly abnormal values (defined as grade 3 or higher) will be presented by intervention group over time. Listing of clinically important laboratory values will be defined according to DMID definitions.

Plots of mean (+/-SE) values and changes from baseline over time for clinically important laboratory parameters will be presented by intervention arm and analysis phase.

Shift tables will be provided summarizing the shift in laboratory values from baseline over time with respect to abnormality criteria (low, normal, high).

Descriptive statistics by toxicity grade over time will be presented. Shift summaries from baseline toxicity grade to the worst toxicity grade will also be presented.

Shift summaries from baseline laboratory value to the worst grade in chemistry and hematology tests will be presented.

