- TE will be concluded if the postbaseline value is above the upper limit and the baseline value is below the upper limit (eg, Normal or Low). The same applies to the postbaseline value being below the lower limit with the baseline value being above the lower limit (eg, Normal or High).
- If the baseline value is missing, a postbaseline abnormality will always be considered as TE.

The number and percentage of participants with treatment-emergent ECG values will be presented by intervention group in analysis phase over time:

- Heart rate (bpm): [ $<50$ ] and [ $>100$ ]
- PR interval (msec): [ $<120$ ] and [ $>200$ ]
- RR interval (seconds): [ $<0.6$ ] and [ $>1.2$ ]
- QRS interval (msec): [ $>120$ ]
- QTcF/ QTcB (msec): [ $>500$ ]

The interpretation of the ECGs as determined by a qualified physician (investigator or qualified designee) will be displayed by the number and percentage of participants meeting the normality criteria. The interpretation will be summarized over time.

Listings will be produced for all ECG data including unscheduled visit data. A listing of clinically relevant ECG abnormalities will also be provided.

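### The visit-window rule keeps one visit per window, not one non-missing result per test, so toxicity-driven safety results can drop out of tables by time point

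*SAP*

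**What the plan says.** SAP 5.1.1 assigns actual visits to the windows of Table 2 (Table 3 for the optional cohort). Its scope is wide: "All efficacy and safety assessments during the investigation phase will be assigned an analysis study day relative to this date". If two or more visits fall in one window, "the visit closest to the target day will be used as the protocol visit for that visit window", and a tie goes to the later visit. The remaining visits are handled so: "The other additional visit(s) will not be used in the summaries or analyses but they can be used for determination of clinically important endpoints". The SAP does not define which endpoints that exception covers.

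The protocol generates results away from scheduled visits:

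- **Liver tests.** After an AST or ALT elevation, protocol 8.2.6 says "AST, ALT, and serum bilirubin should be monitored every 2 weeks until clinically stable".
- **ECGs.** After a confirmed QTcF prolongation, protocol 8.2.3 asks for weekly ECGs and has the confirmatory triplicate recorded on an unscheduled visit form.
- **Early discontinuation.** The Schedule of Activities requires laboratory tests and an ECG at this visit, which footnote f places within 7 days of the decision to stop. Table 2 gives it no window of its own.
- **Vision and hearing.** Footnote y accepts "Audiology and visual examinations within 4 week prior to Day 1 and within 4 days prior or after each visit other than Day 1".
- **Lung function and CT.** The COVID-19 appendix allows this: "Some or all of the lung function assessments, as well as CT scan, may be obtained on a different date from the visit".

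On the output side, SAP 5.6.3.1 presents grade 3 or higher laboratory counts over time and adds: "Shift summaries from baseline toxicity grade to the worst toxicity grade will also be presented". SAP 5.6.3.3 tabulates QTc categories at scheduled time points, treatment-emergent ECG values over time, and QTc increases to the maximum post-baseline value. It mentions unscheduled ECGs once: "Listings will be produced for all ECG data including unscheduled visit data". SAP 5.4.2.2.7 summarizes lung function by visit.

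**The concern.** One value per window is normal for a by-visit mean. The difficulty is that the unit chosen is the visit. A visit can be closest to target and carry no result for the test being tabulated, while a valid result elsewhere in the same window is set aside.

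For safety data this loss is unlikely to be random, because off-schedule tests come mainly from participants with an abnormality. The protocol describes a liver-injury signal for bedaquiline (section 2.2), lists QT prolongation as a known risk (section 2.3.1), and treats liver and heart abnormalities as events of special interest (section 8.3.7). These are the tables that should be complete. Two programmers working from this SAP could also produce different counts.

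**Working it through.** No stated figure of the plan needs reproducing. The check applies the rule to the plan's own windows and schedule.

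**1. Chemistry schedule against windows.** There are 18 post-baseline visits: Weeks 2, 4, 6, 8, 10 and 12 (6), then every 4 weeks from Week 16 to Week 60 (12). The Schedule of Activities has laboratory tests at Weeks 4, 8, 12, 24, 36, 48 and 60, which is 7. Windows without scheduled chemistry: 18 − 7 = 11.

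**2. A single liver test between visits.** The Week 16 window is Days 100–127, target 113. With a scheduled visit on Day 113 and an added liver test on Day 127, the distances are |113 − 113| = 0 and |127 − 113| = 14. Day 113 is kept, with no chemistry. Day 127 is left out.

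**3. An early-discontinuation draw.** With a visit on Day 113 and a discontinuation visit on Day 120, the distances are 0 and 7. Day 113 is kept again, and the Day 120 chemistry is left out.

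**4. Weekly ECGs aligned to the target day.** Days 106, 113, 120 and 127 in the same window have distances 7, 0, 7 and 14. One is kept and three are left out (3/4 = 75%). The same count holds in each window from Week 16 to Week 52. In the 14-day windows (Weeks 4 to 10), two dates fall in the window and one is left out.

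**5. Off-day tests.** In every Table 2 window, a date up to 4 days from the target lies in the same window as a target-day visit. For Week 24 (Days 157–184, target 169), a visit on Day 169 and lung function on Day 172 give distances 0 and 3. If the test is entered as a visit on its own date, Day 169 is kept with no lung-function value.

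**6. Which outputs are exposed.**

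| Output | Effect of the rule |
|---|---|
| Grade 3+ laboratory counts over time; QTc categories by time point; treatment-emergent ECG values over time; by-visit lung function | Directly exposed |
| Worst-grade laboratory shift; increase to maximum post-baseline QTc | Not stated whether additional visits count |
| Adverse-event tables; ECG listings; culture conversion (SAP 5.3.1 expressly uses unscheduled cultures); baseline (last non-missing value before dosing) | Not affected |

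**The case against.** The other side has substantial points.

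- **The exception may cover the tables that matter.** The SAP applies the label clinically important to grade 3+ laboratory values (5.6.3.1) and to abnormal vital signs (Table 5), so the exception could be meant for them. This is a fair reading but not a settled one. The exception is permissive, and none of the safety sections invokes it. Where the authors wanted unscheduled data, for culture conversion and the ECG listing, they said so.
- **Worst-value tables are not expressly windowed.** This stands. For worst grade and maximum QTc the defect is an unanswered question, not a demonstrated loss.
- **ECG is scheduled at every visit.** This also stands. The retained visit normally has an ECG, and weekly ECGs begin only after prolongation is confirmed. Three of four weekly ECGs left out does not mean three of four prolongations missed.
- **Off-day tests may be recorded under their scheduled visit.** If so, no second visit competes and nothing is lost. Footnote y and the COVID-19 appendix are compatible with that. The exposure depends on how dates are entered, which the SAP does not specify.
- **Other safeguards exist.** Clinically relevant laboratory changes are recorded as adverse events, and adverse-event tables do not use these windows. All safety summaries are descriptive (SAP 5.6).

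A reader might also infer a size for the loss. After Week 12, chemistry draws are 12 weeks apart. Assuming uniform onset, an excursion of 4 to 6 weeks would overlap a draw with probability 4/12 to 6/12, leaving 50% to 67% outside one. That is not the share lost. The durations are assumed, and two-weekly testing starts only once an elevation has been found, so many such excursions would go undetected rather than be detected and discarded.

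**Conclusion.** The point holds in limited form. The rule selects by visit, and in 11 of 18 post-baseline windows it can displace a real laboratory result in favour of a visit with none. That follows from the SAP's wording if unscheduled and early-discontinuation assessments count as actual visits, and nothing in the SAP says they do not. Tables by time point are exposed. The worst-grade and maximum-QTc tables are left ambiguous.

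A reader might go further and conclude that worst grade and maximum QTc will be understated, mainly in the bedaquiline arm. The documents do not support this. Those tables are not tied to the selected visit, no rate of unscheduled testing is given, and protocol 2.2.1 also lists AST and ALT increases and liver disorder for rifampicin. Neither the size of the loss nor its direction between arms can be stated. The primary conclusion of the trial is not at risk. This is a cheap improvement to the safety and lung-function reporting.

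**What to change.** Amend SAP 5.1.1 in two places.

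1. For by-visit summaries, choose the closest non-missing result to the target day separately for each parameter within the window.
2. State that worst-grade shifts, overall (any-time) grade 3+ and treatment-emergent abnormality counts, and maximum QTc value and change use all post-baseline results in the analysis phase, including unscheduled and early-discontinuation visits. This names the tables in place of the open-ended exception.

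The cost is two sentences and routine programming, with no change to trial conduct. There is one small downside: participants tested more often have more chances to show an extreme value. A footnote to the affected tables would make that plain.

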## 8. STUDY ASSESSMENTS AND PROCEDURES

### Overview

The Schedule of Activities (SoA) summarizes the frequency and timing of efficacy, PK, and safety measurements applicable to this study.

The following time windows are allowed:

- For visit Weeks 2, 4, 6, 8, 10, and 12 ( $\pm 2$  days)
- For visit Weeks 16, 20, and 24 ( $\pm 3$  days)
- For visit Weeks 28, 32, 36, 40, 44, 48, 52, 56, and 60 ( $\pm 4$  days)

In case of scheduling visit according to above time windows, the investigators should ensure that 4-week sputum collection interval does not fall below 25 days.

All PRO (SGRQ and QOL-B NTM module) assessments should be conducted/completed before any tests, procedures, or other consultations to prevent influencing participant perceptions. The questionnaires will be completed by the investigator after interviewing the participant and the data will be entered into the eCRF by the investigator/study-site personnel. Refer to the PRO completion guidelines for instructions on the administration of PROs.

If multiple assessments are scheduled for the same timepoint, it is recommended that procedures be performed in the following sequence: noninvasive procedures should be collected first before invasive procedure (questionnaire/interview/ECG, vital sign/physical examination/CT scan/audiology/visual examinations/fundoscopy, then sputum sample collection, and blood sampling). ECG and blood collections for PK assessments should be kept as close to the specified time as possible. Other measurements may be done earlier than specified timepoints if needed. Actual dates and times of assessments will be recorded in the source documentation and eCRF.

The total blood volume for the study is approximately 68 to 115.5 mL (52 mL [Group A] for pharmacokinetics and 20 mL [Group B], and 2 mL for pregnancy testing [women of childbearing potential only]).

The total blood volume to be collected from each participant will be approximately 68 to 115.5 mL.

For each participant, the maximum amount of blood drawn from each participant in this study will not exceed 115.5 mL.

Repeat or unscheduled samples may be taken for safety reasons or for technical issues with the samples.

If the unscheduled PK samples are taken, the date and the time of the blood draw must be recorded.

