## IMPORTANT MATTERS RELATED TO COVID-19 AND COORDINATION OF STUDY CONDUCT

- During the course of COVID-19 pandemic, it may not be possible to visit the study site or perform tests as specified in the protocol. Temporary measures may therefore be taken if, in the judgment of the sponsor and the investigator (co-investigator), it is appropriate to continue the subject's study treatment and to maintain the integrity of the study. Specific measures may be required and should be implemented in accordance with applicable local laws, regulations, guidelines and procedures, including:. These deviations will be handled as "COVID-19 -related".
  - If a subject is unable to visit within the acceptable visit window, the subject may visit outside of the visit window.
  - If it becomes necessary to reduce the time spent for tests or if some tests are limited, etc. at the time of visit to the study site, the following actions are acceptable;
    - Sputum collection at the study site: If sputum collection at home is not possible, 2 collections are required at the study site. In such case, if good sputum specimen can be collected at the first time at the study site, no second collection will be acceptable
    - Sputum collection at home: If sputum collection including induced sputum specimen is not possible or limited at the study site, the submission of at least 1 spontaneous sputum specimen collected at home is acceptable without second collection at the study site. And, both sputum specimens at home and at the study site are not obtained and re-collection at home or at the study site is not possible, the submission of sputum specimens at this time point may be omitted
    - If two blood samplings for PK will be drawn at the study site, 2nd blood sampling may be drawn between 30 minutes to 4 hours after the intake. When the timing of 2nd blood sampling is changed, the timing of ECG measurement should be adjusted according to the protocol
    - Assessments of the SGRQ and QOL-B NTM module may be self-administered at home prior to the visit, provided the subject has an environment in place to receive the explanations to his/her queries to these questionnaires. If both assessments are performed after site visit, if only one assessment is feasible, the SGRQ assessment will take precedence and any missing QOL-B NTM module assessment will be allowed

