## Analysis Phase

Analysis phase	Start date	End date
Screening	The date of signing the informed consent	1 day before the first study intervention intake
Investigation	Date of the first study intervention intake	If the participants are from Group A, Min [Week 48, study discontinuation]
		If the participants from Group B will not convert to the optional cohort, Min [Week 60, study discontinuation]
		If the participants will convert to the optional cohort, 1 day before the optional investigation phase
Optional investigation	Date of the first BDQ+CAM+EB intake for nonconverters came from Group B	For nonconverters came from Group B, Min [Optional Week 48, study discontinuation]
Follow-up	If the participants are in Group A and moved to follow-up period, end of the investigation phase + 1 day	Min [Week 60, study discontinuation]

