**Table 2: Visit Windows of Group A/B**

Analysis Phase	Scheduled Visit Number	Time Interval (label on output)	Time Interval (Day)*	Target Time Point (Day)
Screening phase	1	Screening	<1	[-56,0]
Investigation phase	2	Baseline	1	1
	3	Week 2	[2,22]	15
	4	Week 4	[23,36]	29
	5	Week 6	[37,50]	43
	6	Week 8	[51,64]	57

Analysis Phase	Scheduled Visit Number	Time Interval (label on output)	Time Interval (Day)*	Target Time Point (Day)
	7	Week 10	[65,78]	71
	8	Week 12	[79,99]	85
	9	Week 16	[100,127]	113
	10	Week 20	[128,156]	141
	11	Week 24	[157,184]	169
	12	Week 28	[185,212]	197
	13	Week 32	[213,240]	225
	14	Week 36	[241,268]	253
	15	Week 40	[269,296]	281
	16	Week 44	[297,324]	309
Follow-up phase (Group A)/ Investigation phase (Group B)	17	Week 48	[325,352]	337
	18	Week 52	[353,380]	365
	19	Week 56	[381,406]	393
	20	Week 60	[407,425]	421

\*Relative to the date of starting dose in investigation phase

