### **5.3. Primary Endpoint Analysis**

#### **5.3.1. Definition of Endpoint**

The primary endpoint of this study is Sputum Culture Conversion in MGIT at Week 24. Sputum culture conversion is defined as 3 consecutive negative sputum cultures taken at least 25 days apart based on actual collection dates. Sputum cultures at unscheduled visits will also be used for the determination of sputum culture conversion.

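### SAP Table 2 closes the Week 60 analysis window 4 days after target, where comparable visits get 15, so late Week 60 visits in either group have no analysis visit; the follow-up day reference also needs one clarifying line

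*SAP*

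**What the plan says.** **Window limits.** SAP Table 2 gives Week 60 a target of Day 421 and a window of [407,425]. Week 56 is [381,406] with target 393, Week 52 is [353,380] with target 365, and Week 48 is [325,352] with target 337. SAP Table 3 gives Optional Week 48, the optional cohort's last visit, [325,352] with target 337.

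**Protocol tolerance.** Protocol section 8 (Overview) allows 4 days either side "For visit Weeks 28, 32, 36, 40, 44, 48, 52, 56, and 60". The optional cohort schedule gives OPW48 the same 4 days. Section 8 also requires at least 25 days between 4-weekly sputum collections. The COVID-19 appendix adds: "If a subject is unable to visit within the acceptable visit window, the subject may visit outside of the visit window".

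**Day reference.** SAP 5.1.1 opens with "The reference day is Study Day 1", and the footnote to Table 2 reads "Relative to the date of starting dose in investigation phase". The same section then says of Group A follow-up: "All efficacy and safety assessments during the Follow-up (FU) phase will be assigned a day relative to FU start date", with FU ADY = visit date − FU start date + 1. The Analysis Phase table in SAP 5.1 starts follow-up at "end of the investigation phase + 1 day". There is no window table on the follow-up-day scale.

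**Conversion.** SAP 5.3.1 judges conversion "based on actual collection dates" and also uses cultures from unscheduled visits.

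**The concern.** Analysis windows exist because participants do not always keep to the schedule. At most late time points a visit up to 15 days after target is kept. At Week 60 a visit 14 days early is kept, but one 5 days late is not assigned to any visit, although no later window needs the data.

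Week 60 ends the drug-free follow-up in Group A and study treatment in Group B. It is a listed time point for SGRQ, lung function, QOL-B NTM module and, in converters, chest CT. By-visit laboratory, vital sign and ECG summaries also run to it. Late but valid assessments would be missing from these tables.

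The second issue is that SAP 5.1.1 gives two day references for Group A follow-up and does not say what FU ADY is for. In the optional cohort the phase-specific day does drive the windows (Table 3 footnote), so a programmer could carry that pattern over to follow-up. Group B has no follow-up phase, so such an error would fall on one arm only.

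**Working it through.** **1. Reproduce the stated limit.** Target day = 7 × week + 1, so Week 60 = 7 × 60 + 1 = 421. Adding the 4-day tolerance gives 421 + 4 = 425. The SAP limit equals the protocol limit.

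**2. Compare upper margins (window end − target).**

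| Visit | Target | Window | Days past target | Protocol tolerance |
|---|---|---|---|---|
| Week 24 | 169 | [157,184] | 15 | ±3 |
| Week 48 | 337 | [325,352] | 15 | ±4 |
| Week 52 | 365 | [353,380] | 15 | ±4 |
| Week 56 | 393 | [381,406] | 13 | ±4 |
| Week 60 | 421 | [407,425] | 4 | ±4 |
| OPW48 | 337 | [325,352] | 15 | ±4 |

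Weeks 28 to 44 also have 15 days past target with a ±4 tolerance. At Week 60 the lower margin is 421 − 407 = 14 days. Day 425 maps to Week 60; Day 426 maps to no window.

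**3. How a visit can land on Day 426 or later.**
- Under the COVID-19 appendix, which permits out-of-window visits.
- Through the 25-day rule. A visit on Days 401 to 406 is kept as Week 56. The earliest Week 60 visit is then Day 401 + 25 = 426 to Day 406 + 25 = 431, always past the cut-off. If Week 56 is within tolerance (latest Day 397), 397 + 25 = 422, which still fits.

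**4. Size.** With the same 15-day margin the window would end at 421 + 15 = 436, recovering Days 426 to 436. The documents give no late-visit rate. If 5% to 10% of Week 60 visits fall on those days (an assumption), the same 5% to 10% of Week 60 by-visit data are lost. With the planned 62 per group as a ceiling, that is at most 62 × 0.05 = 3.1 to 62 × 0.10 = 6.2 participants per group. Fewer will reach Week 60, because Group A non-converters leave at Week 48 and some of Group B move to the optional cohort.

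**5. Day reference.** Take the Week 48 visit on Day 337, so follow-up starts on Day 338.

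| Visit | Day from first dose | Table 2 on first-dose day | FU ADY | Table 2 if FU ADY were entered |
|---|---|---|---|---|
| Week 52 | 365 | Week 52 | 365 − 338 + 1 = 28 | Week 4 |
| Week 56 | 393 | Week 56 | 393 − 338 + 1 = 56 | Week 8 |
| Week 60 | 421 | Week 60 | 421 − 338 + 1 = 84 | Week 12 |

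Over all visit days within tolerance, with at least 25 days between Weeks 48 and 52, FU ADY runs 25–36, 48–64 and 76–92. None reaches a Week 52–60 window. Using the first-dose day, as the footnote says, every one of those visits goes to its correct window.

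**The case against.** The best defence of Day 425 is that it is exactly the protocol limit, so every Week 60 visit within tolerance is kept in both groups. Only deviating visits fall outside, and the COVID-19 appendix treats such visits as deviations without promising them a place in by-visit tables. A Week 56 visit on Days 401 to 406 is itself outside the protocol's tolerance. All of this is true, so the cut-off does not contradict the protocol. It does not explain why Week 48 and OPW48, with the same tolerance, get 15 days, and OPW48 is also a last visit.

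A fair caution concerns widening: study treatment in Group B ends at Week 60 and later care is at the investigator's discretion. An open-ended window could mix differently treated data into Week 60. That argues for a bounded extension.

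On the day reference, a reader might infer that Group A visits at Weeks 52 to 60 are misassigned under the plan as written. The documents do not support that. The Table 2 footnote fixes the first-dose scale, the table holds follow-up rows on that scale, and the follow-up sentence only assigns a day; it does not say to enter that day in Table 2. A reader might also infer that the Day 425 limit drops Week 52 or Week 56 visits, or affects Group A only. It does neither.

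**Conclusion.** The Week 60 cut-off is a stated rule that excludes data the SAP would keep at comparable visits. It affects visits on Day 426 or later, in both groups. The loss is one for one with the fraction of late visits, which the documents do not give.

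The affected outputs are descriptive. Adverse event incidence does not depend on visit windows, and the Week 24 primary endpoint is untouched. The planned between-group test at Week 60, on MGIT conversion, is largely protected by the use of actual collection dates and unscheduled cultures. The SAP does not say whether a culture after Day 425 counts toward conversion at Week 60.

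The two day references are a real ambiguity in the text, but they cause misassignment only if FU ADY is used against the Table 2 footnote. That part calls for clarification, not correction of an error. The arithmetic assumes that the investigation phase in Group A ends at the Week 48 visit.

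**What to change.** 1. In SAP Table 2, change the Week 60 window from [407,425] to [407,436], matching the 15-day margin elsewhere. The existing closest-to-target rule handles multiple visits. Do not leave the window open-ended.
2. In SAP 5.1.1, state that Table 2 windows use the day from first dose for all visits, including Group A follow-up, and that FU ADY is for listings only.
3. State whether a culture collected after Day 425 can count toward conversion at Week 60.

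The cost is one table cell and a few sentences, to be documented before the Week 60 data are analysed. The small downside is that a few visits up to 15 days after target, possibly after Group B study treatment has ended, will be included in Week 60.
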